9.4.7 Description of efficacy variables

Efficacy parameters are described in [Section 8.1](#). The derivation of baseline results is described in [Section 9.4.3.2](#).

The analysis of the efficacy markers will be based on the mITT population. As a sensitivity analysis, the primary endpoint will also be analyzed based on the intent-to-treat (ITT) population. Secondary endpoints analysis might be run on the ITT population as sensitivity analysis in case an important number of patients using rescue therapy is observed.

Sub-group analyses might be done, if deemed appropriate.

If relevant, based on results obtained on planned analyses (eg, if any trend or signal is observed), further exploratory analyses could be conducted, using statistical models for instance.

Analysis

Table 4 - Efficacy analyses

| Endpoint | Statistical analysis methods |
|------------------|--|
| Primary | 
Change from baseline on Week 17 for intraepidermal nerve fiber density by PGP9.5 antibody staining in lesional skinChange from baseline on Week 17 for intraepidermal nerve fiber branching by PGP9.5 antibody staining in lesional skinRaw data and change from baseline to Week 17; ie, absolute and percent changes, will be summarized with descriptive statistics (such as mean, median, SD, minimum, maximum, and 90% confidence interval) and plots for AD participants based on the mITT population |
| Secondary | 
Changes from baseline on Weeks 3 and 21 for intraepidermal nerve fiber density by PGP9.5 antibody staining in lesional skinChanges from baseline on Weeks 3 and 21 for intraepidermal nerve fiber branching by PGP9.5 antibody staining in lesional skinRaw data and changes from baseline to Week 3 and Week 21; ie, absolute and percent changes, will be summarized with descriptive statistics (such as mean, median, SD, minimum, maximum, and 90% confidence interval) and plots for AD participants based on the mITT populationProfiles for baseline to Week 21 time points will be generated for individual values: eg, spaghetti plot and boxplot, and patients' group meansChanges from baseline over time and at weeks 17 and 21 for the outcomes of the following assessments/questionnaires
Peak pruritus assessed by numeric rating scale (NRS)Eczema and severity index (EASI)Scoring Atopic Dermatitis (SCORAD)Patient-Reported Outcomes Measurement Information (PROMIS-itch)Patient Oriented Eczema Measure (POEM)Dermatology Life Quality Index (DLQI)Atopic Dermatitis Control Tool (ADCT)Sleep quality NRSSkin Pain NRSSkin Sensitivity NRSSkin Burning NRSRaw data and change from baseline; ie, absolute and percent changes, will be summarized with descriptive statistics (such as mean, median, SD, minimum, maximum, and 90% confidence interval) for AD participants based on the mITT populationProfiles for baseline to Week 17, and baseline to Week 21 time points will be generated for individual values: eg, spaghetti plot and boxplot, and patients' group meansProportion of AD participants reaching pruritus NRS ≥ 4 point improvement from baseline at Weeks 3, 5, 9, 17 and 21
Number and percentage of AD participants reaching pruritus NRS ≥ 4 point improvement from baseline will be reported by time points based on the mITT populationBarplot over time of proportion of AD participants reaching pruritus NRS ≥ 4 point improvement from baseline will be produced. |

| Endpoint | Statistical analysis methods |
|---|---|
| Exploratory | |
| | |
| 
• Nanostring-Digital Spatial Profiling (N-DSP) for epidermal proteins and RNA changes from baseline in lesional skin on Weeks 3, 17, and 21• Neuromarkers changes from baseline on Weeks 3, 17, and 21 in lesional skin (detected by immunohistochemistry, RNA in situ hybridization and/or RT-qPCR):
- NGF- NK-1R- MRGPRX1/2/4- TRPV1/A1- SEMA3A- integrin alpha 6- periostin- ANO1- NTRK1- NRTN- IL-4- IL-13- IL-31- Mast cells, basophils, eosinophils, keratinocytes, macrophages and lymphocytes• Neuronal architecture in lesional skin biopsies from AD patients and skin biopsies from healthy controls at baseline• Neuromarkers in lesional skin biopsies from AD patients and skin biopsies from healthy controls at baseline• Neuronal architecture in lesional and non-lesional skin biopsies from AD patients at baseline• Neuromarkers in lesional and non-lesional skin biopsies from AD patients at baseline• Neuronal architecture, Nanostring derived parameters and neuromarkers changes from baseline and clinical assessments changes from baseline | 
• Data will be summarized with descriptive statistics. Univariate analysis on raw data and changes from baseline for each parameter and multivariate unsupervised analysis (eg hierarchical clustering) will be performed as appropriate based on the mITT population• Data will be summarized with descriptive statistics. Univariate analysis on raw data and changes from baseline for each parameter and multivariate unsupervised analysis (eg hierarchical clustering) will be performed as appropriate based on the mITT population• Descriptive statistics and plots will be produced for AD participants and healthy participants at baseline based on the mITT population• Descriptive statistics and plots will be produced for lesional and non-lesional skin biopsies from AD participants at baseline based on the mITT population• Scatterplot to visualize the form of the relationship between changes from baseline will be produced for AD participants at specific timepoints, based on the mITT population• Pearson or Spearman's rank correlation coefficients and p-values will be reported at each defined time points based on the mITT population• A heatmap of the change from baseline of some key biomarkers could be used to have an overall representation of the evolution of those biomarkers over time in AD participants |

| Endpoint | Statistical analysis methods |
|----------|--|
| | 
As an exploratory analysis repeated measures correlation method might be used to assess the overall correlations overtime (20) |

Abbreviations: AD: atopic dermatitis; mITT: modified intent-to-treat; SD: standard deviation.

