8.1.1.9 Sleep quality numerical rating scale

Sleep quality NRS is a one-item PRO measure asking patients to rate the quality of their sleep using a 0 (“Worst possible sleep”) to 10 (“Best possible sleep”) NRS. Patients will be asked to complete the following question upon awakening:

“Select the number that best describes the quality of your sleep last night.”

The Sleep Quality NRS will be assessed at time points according to [Section 1.3](#).

The sleep quality NRS is provided in the study reference manual.

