8.3.2 Neuroanatomy/Neuronal architecture

#A skin biopsy samples will be investigated for epidermal neuroanatomy/neuronal architecture. Briefly, the PFA-fixed part of the biopsies will be used to analyze the epidermal nerve fiber density and anatomy. Nerve fibers will be visualized by staining consecutive sections for the pan-axonal marker protein gene product 9.5 (PGP9.5); the basement membrane will be visualized by staining for collagen type 4 in order to determine exactly the point of invasion of nerve fibers into the epidermis.

Quantification of intraepidermal nerve fiber density will be calculated by assessing nerve fibers crossing the basement membrane per square millimetre (F/mm²).

Branching of epidermal nerve fibers will be assessed semi-quantitatively by classifying patients into 4 groups comprised of only linear, mainly linear, mainly branched or only branched fibers.

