9.2 SAMPLE SIZE DETERMINATION

Sample size for this exploratory study was determined based on medical experts' input/clinical judgement. No formal sample size estimation was conducted. Approximately 10 to 12 evaluable AD participants per site might be enough to provide interpretable data and meet study primary objective.

Neuronal architecture and neuromarkers data collected from skin biopsy in similar settings as planned for this study were not available: ie, expected changes from baselines in neuronal architecture and neuromarkers after 16-week treatment with dupilumab in AD participants with chronic pruritus are unknown.

Allowing for a drop-out rate of 20%, a total of approximately 34 AD participants with chronic pruritus will be enrolled to achieve a minimum of 12 evaluable AD participants per country, ie, participants with no major or critical deviations related to IMP and/or biomarker measurements, for whom the biomarker data for primary analysis, ie, neuronal architecture and neuromarkers data from skin biopsy at baseline and Week 17, are considered sufficient and interpretable.

Up to 10 healthy participants (with a minimum of 3 per country) serving as a reference comparator group will be enrolled. Healthy participants will be matched with AD participants, as far as possible, according to site, age, gender, race, location of targeted lesional and non-lesional skin area.

Drop-out rate in healthy participants is expected to be minimal.

Any drop-out participant will not be replaced.

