1.2.6.1 Primary endpoints

The two primary endpoints (intraepidermal nerve fiber density and branching by PGP9.5 antibody staining in lesional skin) was planned to be analyzed as quantitative endpoints. But the branching is a semi-quantitative endpoint with 4 modalities: “only linear”, “mainly linear”, “mainly branched” and “only branched” fibers. The statistical method will be updated as follows:

- The number and percentage of participants for each modality will be described by timepoints, by skin type (Lesional pruritic skin, Post-lesional healed skin non-pruritic non-lesional, Lesional non-pruritic skin and Non-lesional skin) and by treatment group based on the mITT and ITT population. Only the evaluable participants will be taken into account in the calculation of the percentages.
- The listing of individual data will be performed, including the following information: demographic data, location, laterality and directionality...
- No plots will be performed.

To analyze the change from baseline on Week 17 for intraepidermal nerve fiber density by PGP9.5 antibody staining in lesional skin, the summary plots for AD participants based on the mITT population (and on the ITT population) will be graphs of mean +/- standard error of the mean (SEM) for raw data, absolute and percent change from baseline at baseline (ie, 0) and Week 17.

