1.3 DATA HANDLING CONVENTIONS

This section describes the rules and conventions used in the presentation and analysis of data.

In the statistical appendices and in-text tables, the following study group label will be used:

- Healthy Participant.
- Dupilumab (*identified as “patient group” in the protocol*).

All individual data for all included participants will be presented in data listings, sorted by study group and participant number.

In listings, no date of assessments/events/medications will be presented but only the relative day. It will be calculated as follows:

- For AD participants: relative day = date of assessments/events/medications – date of first IMP administration +1.
- For healthy participants: relative day = date of assessments/events/medications – date of D1 visit +1.

For parameters with evaluations before administration and in cases of rechecked value(s) for one participant, only the last observation will be used as baseline in descriptive statistics and derivations of other parameter values. After baseline, only observations planned in the protocol will be used in descriptive statistics.

If not otherwise stated in the statistical section of the protocol:

- Missing data other than protocol-planned baseline values will not be replaced.
- Descriptive statistics for quantitative parameters will be provided using number of observations (N), mean, standard deviation (SD), SEM, median, minimum and maximum. The 95% confidence interval will be added for efficacy analyses.
- Descriptive statistics for qualitative parameters will be provided using frequencies (N) and percent (%).

Handling missing data for adverse events

In case of missing or inconsistent information, an AE will be counted as a treatment-emergent AE (TEAE), unless it can clearly be ruled out that it is not a treatment-emergent adverse event (eg, by partial dates or other information).

If the start date (or time) of an AE is incomplete or missing, it will be counted as TEAE except if an incomplete date (or time) or comment indicates that it is a pre- or post-treatment event.

If the relationship to study intervention is missing for an AE, this AE will be assessed as unrelated if it started before administration of study medication; in all other cases it will be assumed to be related.

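### The mean percent change in nerve fiber density, with its interval and SEM plot, reads above zero when nothing changes, and percent change has no value for scales that can start at 0

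*Protocol*

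**What the plan says.** Protocol Section 8.3.2 defines the density measure: "Quantification of intraepidermal nerve fiber density will be calculated by assessing nerve fibers crossing the basement membrane per square millimetre". It is a count per area, so it cannot fall below zero.

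For the primary endpoint, Protocol Table 4 states "change from baseline to Week 17; ie, absolute and percent changes, will be summarized with descriptive statistics (such as mean, median, SD", and continues with "minimum, maximum, and 90% confidence interval) and plots for AD participants based on the mITT population". The secondary part of the table repeats this for density at Weeks 3 and 21. SAP 1.2.6.1 specifies the plots as "graphs of mean +/- standard error of the mean (SEM) for raw data, absolute and percent change from baseline", and SAP 1.2.6.2 does the same for Weeks 3 and 21. SAP 1.3 adds "The 95% confidence interval will be added for efficacy analyses", but only where the protocol's statistical section does not say otherwise, so the protocol's 90% level governs here.

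For the questionnaires, Table 4 again states "change from baseline; ie, absolute and percent changes, will be summarized with descriptive statistics". This covers every listed scale, including the skin pain, skin sensitivity, skin burning and sleep quality NRS.

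Neither document writes out a percent-change formula or says what happens when the baseline is 0.

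**The concern.** Percent change divides by the baseline reading, which carries its own measurement and sampling variation. A low baseline reading gives a very large rise, while a fall can never exceed 100%. Averaging across participants does not cancel this asymmetry.

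The sleep scale (0 worst, 10 best) shows the mechanism. One participant moving from 1 to 8 scores (8 − 1)/1 = +700%. Another moving from 8 to 1 scores (1 − 8)/8 = −87.5%. The mean absolute change of the pair is 0, but the mean percent change is (700 − 87.5)/2 = about +306%.

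For density, a reader of the percent table or its plot could see regrowth where there is none, or an understated fall. The design is single-arm, and healthy participants are biopsied once (Protocol 1.4), so no comparison group shows the drift. Protocol 9.2 says that the expected changes are unknown, so a reader has no external yardstick either. The findings are meant to guide the design of a larger study (Protocol 2.2).

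For scales without an entry minimum, a participant at 0 has no percent change. That person leaves the percent table but stays in the absolute table. On pain, sensitivity and burning, those at 0 can only stay or worsen, so their loss flatters the percent table. On sleep quality, those at 0 can only stay or improve, so the effect runs the other way.

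**Working it through.** **Inputs from the documents.** Protocol 9.2: "Allowing for a drop-out rate of 20%, a total of approximately 34 AD participants with chronic pruritus will be enrolled". Evaluable number: 34 × 0.8 = 27.2, so n = 27 (check: 27/0.8 = 33.75, rounded up to 34). The plan gives no expected percent change, SD, CV or correlation, so it has no figure of its own to reproduce.

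**Assumptions.** Baseline reading X and Week 17 reading Y are log-normal with the same CV, 0.2 to 0.5, and log-scale correlation ρ from 0 to 0.7.

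**Direction, without a distribution.** If nothing changes, X and Y are positive and exchangeable, so Y/X and X/Y have the same distribution. Then E[Y/X] = E[(Y/X + X/Y)/2] ≥ 1, because r + 1/r ≥ 2 for any positive r. The mean percent change is above 0 whenever X and Y differ within a person. A larger sample does not reduce this.

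**Size.** With s² = ln(1 + CV²), the expected mean percent change under no change is 100 × [exp(s²(1 − ρ)) − 1] = 100 × [(1 + CV²)^(1 − ρ) − 1].
- CV 0.2, ρ = 0.7: 1.04^0.3 − 1 = +1.2%
- CV 0.5, ρ = 0: 1.25 − 1 = +25.0%

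**Interval behaviour.** Simulation of 40,000 no-change trials, n = 27, t-based 90% interval. The share wholly above zero should be 5%.

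| CV | Drift, ρ = 0.7 | Drift, ρ = 0 | Above zero, ρ = 0.7 | Above zero, ρ = 0 |
|---|---|---|---|---|
| 0.2 | +1.2% | +4.0% | 9.1% | 14.0% |
| 0.3 | +2.6% | +9.0% | 11.4% | 20.3% |
| 0.4 | +4.6% | +16.0% | 14.7% | 27.8% |
| 0.5 | +6.9% | +25.0% | 18.1% | 34.6% |

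At the 95% level the share is 4.7% to 19.6% over the same range, against 2.5%.

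**A true 20% fall, independent readings (ρ = 0).** The expected reading is 0.8 × (1 + CV²) − 1: −16.8%, −12.8%, −7.2% and 0.0% at CV 0.2, 0.3, 0.4 and 0.5. The 90% interval lies wholly below zero in about 95%, 55%, 24% and 11% of trials. For the log ratio the figures are about 99%, 86%, 67% and 52%.

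**The alternatives under no change, same range.** Mean absolute change averages 0, and its 90% interval excludes 0 in about 10% of trials, as it should. The mean log ratio does the same. Median percent change averages about +0.1% to +1.3%.

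**Zero baselines.** Section 5.1.1 of the protocol requires EASI of at least 12 and pruritus NRS of at least 4 at baseline, so neither can be 0. It sets no minimum for skin pain, sensitivity, burning or sleep quality NRS, all of which start at 0 (Protocol 8.1.1.6 to 8.1.1.9). Nor does it set one for POEM (0 to 28), DLQI (0 to 30) or ADCT (0 to 24). How many participants start at 0 is not given. If a share p do, 34p have no percent change, and the chance of at least one is 1 − (1 − p)^34:
- p = 5%: 1.7 participants; 83%
- p = 10%: 3.4 participants; 97%
- p = 20%: 6.8 participants; more than 99%

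**The case against.** The study is exploratory and descriptive. No hypothesis test, power statement or decision rule rests on the percent-change interval, so a one-sided error rate judges it as a test that the plan does not run. Raw data, absolute change and the median are planned alongside, and SAP 1.2.6.1 plots absolute change too. The variability is assumed, and at its low end the drift is only about 1%. The log-scale interval performs exactly as it should partly because the simulated data are log-normal. SAP 1.3 requires the number of observations with quantitative summaries, so a smaller N in a percent table would be visible. A log ratio needs its own rule if a density is zero.

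Most of this stands, and it limits the weight of the point. It does not remove it. With no test planned, the estimates, intervals and plots are the result, and the interval and plot on the percent scale attach to the mean, not the median. The direction of the drift needs no log-normal assumption. A visible N shows that participants are missing from a table but not why.

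Three stronger readings are tempting, and the documents do not support them.
- A reader might infer that the primary density result as a whole is biased. It is not: the mean absolute change is unbiased under no change and is already planned.
- A reader might infer that the zero-baseline problem covers every NRS. Peak pruritus has an entry floor of 4.
- A reader might infer that it also covers the PROMIS-itch items. Neither document gives their response range, so a score of 0 cannot be shown to be possible.

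**Conclusion.** The point holds, confined to the mean percent change in density, its confidence interval and its SEM plot. Under no change these drift upward, by about +1% to +25% over the assumed CV and correlation ranges. The nominal 90% interval lies wholly above zero in about 9% to 35% of trials with 27 evaluable participants. With independent readings, a true 20% fall reads as about −17% to 0%. The direction is certain given any within-person variation; the size rests wholly on the assumed variability.

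The missing zero-baseline rule is a smaller, separate gap. It is definite for the four NRS scales without an entry minimum, and potential for POEM, DLQI and ADCT, where a total of 0 at entry is possible on the scale but may be rare in this population.

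This should be fixed, but it does not undermine the study: the absolute-change summary already answers the primary objective without this bias.

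**What to change.** In Protocol Table 4 and SAP 1.2.6.1 and 1.2.6.2:

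- **Density, Weeks 3, 17 and 21.** Name absolute change as the lead summary. Replace the mean percent change, its interval and its SEM plot by the geometric mean ratio of follow-up to baseline, with a confidence interval from the log ratio. State in advance that, if any density is zero, 100 × mean(change)/mean(baseline) with a bootstrap interval is used instead. This avoids adding an arbitrary constant to zero counts.
- **Skin pain, sensitivity, burning and sleep quality NRS.** Report absolute change only.
- **POEM, DLQI and ADCT.** Lead with absolute change. If percent change is kept, report the number excluded for a zero baseline.
- **EASI and peak pruritus NRS.** Percent change may stay, because both have an entry minimum.

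The cost is SAP wording and some extra programming, with no new data. The drawback is a relative measure that is less familiar to some readers than percent change.

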9.4.8 Safety analyses

The safety evaluation will be based on the review of vital signs parameters and reported AEs. The safety analysis will be conducted according to the Sponsor's document "Analysis and reporting of safety data from Clinical Trials through the CSR" (BTD-009536).

All the safety analyses will be performed using the safety population. When applicable, results will be by groups and overall.

9.4.8.1 Adverse events

9.4.8.1.1 Definitions

Adverse events will be coded to a "Preferred Term (PT)" and "High Level Group Term (HLGT)", "High Level Term (HLT)" and primary "System Organ Class (SOC)" using the Medical Dictionary for Regulatory Activities (MedDRA, version currently in use by the Sponsor at the time of database lock).

For AD participants' group, they will be classified into predefined standard categories according to chronological criteria:

- Pre-treatment AEs: AEs that occurred, worsened or became serious during the pre-treatment period defined as the time between informed consent signature and the first IMP administration.
- Treatment-emergent AEs (TEAEs): AEs that occurred, worsened or became serious during the TEAE period defined as the time from the first IMP administration up to the EoT Visit (EoT included).
- Post-TEAEs: AEs that occurred, worsened or became serious during the post-TEAE period defined as the time starting after the TEAE period (including the follow-up period).

Treatment-emergent AEs will be assigned to the treatment received at the time of the AE onset.

If the onset date (or time) of an AE (occurrence, worsening or becoming serious) is incomplete or missing, then the AE will be considered as a TEAE unless a partial date (or time) shows it as a pre- or post-treatment event.

For all healthy participants, safety data will be considered as part of a single period starting with the signature of the informed consent and ending with the EoS Visit (EoS included).

All AEs reported in the study will be listed, sorted by participant, onset date and time.

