| 
Assess change in neuronal architecture following long term treatment with dupilumab in skin biopsies from AD participants with chronic pruritus | 
Change from baseline on Week 17 for intraepidermal nerve fiber density by protein gene product 9.5 (PGP9.5) antibody staining in lesional skinChange from baseline on Week 17 for nerve fiber branching by PGP9.5 antibody staining in lesional skin |
| Secondary | |
| 
Assess change in neuronal architecture following short term treatment with dupilumab and during follow-up in skin biopsies from AD participants with chronic pruritusTo evaluate the efficacy of dupilumab in AD participants with chronic pruritus | 
Changes from baseline on Weeks 3 and 21 for intraepidermal nerve fiber density by PGP9.5 antibody staining in lesional skinChanges from baseline on Weeks 3 and 21 for nerve fiber branching by PGP9.5 antibody staining in lesional skinChanges from baseline over time and at Weeks 17 and 21 for the outcomes of the following assessments/questionnaires:
Peak pruritus assessed by numeric rating scale (NRS)Eczema and severity index (EASI)Scoring Atopic Dermatitis (SCORAD)Patient-Reported Outcomes Measurement Information (PROMIS-itch)Patient Oriented Eczema Measure (POEM)Dermatology Life Quality Index (DLQI)Atopic Dermatitis Control Tool (ADCT)Sleep quality NRSSkin Pain NRSSkin Sensitivity NRSSkin Burning NRSProportion of AD participants reaching pruritus NRS ≥ 4 point improvement from baseline at Weeks 3, 5, 9, 17, and 21 |
| 
To evaluate the safety of dupilumab in adult participants with moderate-to-severe AD | 
Incidence of treatment-emergent adverse events during the treatment and follow-up period |

Overall design:

- Open-label, multi-center, single-arm, non-controlled, exploratory study.
- Moderate-to-severe AD participants with chronic pruritus (N=34) and healthy participants (up to N=10, will serve as control group providing normal skin reference for baseline skin biopsy derived endpoints; matched for gender, age, race and anatomical site of skin biopsy).

- A 20-week Observation Period including 16 weeks of treatment for AD participants and a 4-week follow-up period.
- Loading dose of 600 mg dupilumab followed by 300 mg every 2 weeks (Q2W).

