3 OBJECTIVES AND ENDPOINTS

Table 1 - Objectives and endpoints

| Objectives | Endpoints |
|--|---|
| Primary | |
| 
Assess change in neuronal architecture following long term treatment with dupilumab in skin biopsies from AD participants with chronic pruritus | 
Change from baseline on Week 17 for intraepidermal nerve fiber density by protein gene product 9.5 (PGP9.5) antibody staining in lesional skinChange from baseline on Week 17 for nerve fiber branching by PGP9.5 antibody staining in lesional skin |
| Secondary | |
| 
Assess change in neuronal architecture following short term treatment with dupilumab and during follow-up in skin biopsies from AD participants with chronic pruritusTo evaluate the efficacy of dupilumab in AD participants with chronic pruritus | 
Changes from baseline on Weeks 3 and 21 for intraepidermal nerve fiber density by PGP9.5 antibody staining in lesional skinChanges from baseline on Weeks 3 and 21 for nerve fiber branching by PGP9.5 antibody staining in lesional skinChanges from baseline over time and at Weeks 17 and 21 for the outcomes of the following assessments/questionnaires:
Peak pruritus assessed by numeric rating scale (NRS)Eczema and severity index (EASI)Scoring Atopic Dermatitis (SCORAD)Patient-Reported Outcomes Measurement Information (PROMIS-itch)Patient Oriented Eczema Measure (POEM)Dermatology Life Quality Index (DLQI)Atopic Dermatitis Control Tool (ADCT)Sleep quality NRSSkin Pain NRSSkin Sensitivity NRSSkin Burning NRSProportion of AD participants reaching pruritus NRS ≥ 4 point improvement from baseline at Weeks 3, 5, 9, 17, and 21 |
| 
To evaluate the safety of dupilumab in adult participants with moderate-to-severe AD | 
Incidence of treatment-emergent adverse events during treatment and follow-up period |
| Exploratory | |
| 
Assess change in neuromarkers following treatment with dupilumab in skin biopsies from AD participants with chronic pruritus | 
Nanostring-Digital Spatial Profiling (N-DSP) for epidermal proteins and RNA changes from baseline in lesional skin on Weeks 3, 17, and 21 |

| Objectives | Endpoints |
|--|--|

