9.4.8.1.2 Treatment-emergent adverse events

The following TEAEs summaries will be provided for the patient's group of the safety population:

Overview of TEAEs: number and percentage of subjects with any TEAE, any serious TEAE, any TEAE leading to death (if any occurred), any TEAE leading to permanent treatment discontinuation, and any TEAE of special interest.

- Summary of TEAEs by primary SOC and PT:
 - Number and percentage of patients with at least 1 TEAE;
 - Number of occurrences of TEAEs.

Patients presenting TEAEs will be listed sorted by primary SOC and PT. By definition, no TEAEs summary will be displayed for healthy participants.

AEs that occur outside the treatment-emergent period or in healthy participants will be summarized separately.

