1.2.1 Observation period definition

For the AD participants, the overall observation period will be divided into 3 segments as follows:

- The pre-treatment period is defined as the period up to the first investigational medicinal product (IMP) administration.
- The treatment-emergent (TE) period is defined as the period from the IMP administration up to the end of treatment (EOT) visit (included).
- The post-treatment period (ie, the follow-up extension period) is defined as the period from the end of the TE period.

For the healthy participants, the overall observation period will be divided into 2 segments as follows:

- The screening period is defined as the period of 21 days up to the collection of the skin biopsy.
- The observational period is defined as the period of 7 days following collection of the skin biopsy.

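### The secondary safety endpoint names treatment and follow-up, but the TEAE tables stop at end of treatment and no combined participant proportion is described

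*Protocol*

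**What the plan says.** **Endpoint.** Protocol Section 3, Table 1 gives the secondary safety endpoint as "Incidence of treatment-emergent adverse events during treatment and follow-up period". The synopsis (Section 1.1) has "Incidence of treatment-emergent adverse events during the treatment and follow-up period". Protocol 4.1 runs follow-up from Week 17 to Week 21. The synopsis agrees: four weeks after end of treatment (EoT), within an observation period of up to 20 weeks.

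**Analysis periods.** Protocol 9.4.8.1.1 has the TEAE period "defined as the time from the first IMP administration up to the EoT Visit (EoT included") and the post-TEAE period "defined as the time starting after the TEAE period (including the follow-up period"). SAP 1.2.1 makes the same split. Its treatment-emergent period is "the period from the IMP administration up to the end of treatment (EOT) visit (included"), and it adds: "The post-treatment period (ie, the follow-up extension period) is defined as the period from the end of the TE period".

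**Outputs.** Protocol 9.4.8.1.2 plans a TEAE overview and a table by system organ class and preferred term (SOC/PT), both with counts and percentages. Section 9.4.8.1.5 tabulates treatment-emergent events of special interest (AESIs). For everything else, 9.4.8.1.2 says: "AEs that occur outside the treatment-emergent period or in healthy participants will be summarized separately". Section 9.4.8.1.1 adds: "All AEs reported in the study will be listed, sorted by participant, onset date and time". The SAP describes no further adverse event table and refers to the sponsor's reporting standards for layout.

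**The concern.** The endpoint and the definition behind its tables do not agree. Under 9.4.8.1.1, an event with a known onset after EoT cannot be treatment-emergent, so the endpoint's reference to follow-up has no content. SAP 1.2 lists changes and clarifications to the protocol's statistical section, but it repeats the split and leaves the mismatch in place.

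A reader who takes the TEAE overview as the endpoint result sees the treatment period only, although Protocol 4.1 describes Weeks 17 to 21 as a period for collecting safety data. Anyone wanting the figure over both periods would have to build it from the listing, with no pre-specified counting rule.

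**Working it through.** The documents state no expected incidence for this endpoint, so there is no figure to reproduce. The check compares the two windows and then asks whether the planned outputs give the endpoint's number.

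**1. Windows.** Inputs from the schedule of activities (Protocol 1.3): first dose Day 1, EoT Day 113, end of study (EoS, Week 21) Day 141.

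- Named by the endpoint, first dose to EoS: 141 − 1 = 140 days (20 weeks).
- Covered by the TEAE period, first dose to EoT: 113 − 1 = 112 days (16 weeks).
- Outside the TEAE period: 141 − 113 = 28 days, and 28/140 = 20.0%.

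Counting Day 1 as a full day gives 28/141 = 19.9%, which changes nothing.

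**2. One exception.** Protocol 9.4.8.1.1 and SAP 1.3 count an event with a missing or incomplete onset date as a TEAE unless other information rules this out. Some follow-up events could enter the TEAE tables this way, but that does not create a combined proportion.

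**3. Can the separate summaries be combined?** Let x participants have a TEAE and y have a follow-up event, out of N = 34 (the planned number, assuming all are dosed). The number with an event in either period lies between max(x, y) and min(N, x + y). So x/N + y/N is only an upper bound.

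Illustration with assumed counts x = 15 and y = 5:

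- Treatment period: 15/34 = 44.1%.
- Follow-up: 5/34 = 14.7%.
- Combined: from 15/34 = 44.1% to 20/34 = 58.8%.

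The two percentages leave a range of 14.7 points. Overlap is to be expected, because 9.4.8.1.1 classes events by whether they began, worsened or became serious in a period. One participant, and even one event, can therefore appear in both.

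**4. Per participant.** Each participant whose only event falls in follow-up adds 1/34 = 2.9 percentage points to the combined figure. The documents do not say how many to expect.

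**5. Where the combined figure could come from.** The all-event listing carries participant and onset, so the count can be derived. Protocol 9.4.8 asks for results by group and overall, but that reads as pooling study groups, not periods. No table in either document pools the two periods.

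**The case against.** The strongest reply is that nothing is missing. The endpoint does not literally ask for one pooled proportion. Treatment-period incidence is tabulated, later events are summarized separately, every event is listed, and deaths and serious events are listed without restriction to the TEAE period. The sponsor's reporting standards, cited in Protocol 9.4.8 and SAP 1.1, may include a pooled table. The study is single-arm and tests no hypothesis.

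Most of this stands. Follow-up events are reported, a pooled table in the templates cannot be excluded, and no between-group comparison is affected. What remains is that the endpoint and the definition contradict each other in writing. A template would not resolve that.

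The EoT cut-off is also coherent in itself. Protocol 9.4.4.1 defines exposure as last dose minus first dose plus 14 days. With the last scheduled dose on Day 99, that is 99 − 1 + 14 = 112 days, which matches first dose to EoT. A reader might infer that the TEAE period is wrong and should be extended to Week 21. The documents do not support that. Extension would break the match with exposure, and it would widen both the missing-date rule and the vital-sign abnormality window in Protocol 9.4.8.2.

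**Conclusion.** The point holds as a mismatch between endpoint and analysis, of minor weight. On scheduled visit days, 28 of the 140 days named by the endpoint (20%) lie outside the TEAE tables. This is a share of time, not of events, and it applies to participants whose EoT falls at Week 17. Neither document describes the combined participant proportion, and it cannot be recovered from the two period percentages. It can be derived from the listing.

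Three stronger readings are tempting but not supported:

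- **Follow-up events go unreported.** They are listed and summarized separately.
- **The gap is 84 of 196 days (42.9%), up to the Week 29 call on Day 197.** This needs Week 29 to count as follow-up, which rests only on a column header in the schedule. Protocol 4.1 and the synopsis define follow-up as the four weeks after EoT, and the call comes after EoS.
- **The gap is larger by a known amount for early stoppers.** Footnote b of the schedule moves their EoT assessments to discontinuation but also asks them to complete the remaining visits, so no size can be given. The conflict between Protocol 6.6 and 7.1.1 on whether they stay in the study is a separate matter that the protocol must reconcile.

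**What to change.** 1. Keep EoT as the end of the TEAE period in Protocol 9.4.8.1.1 and SAP 1.2.1.
2. Reword the endpoint in the synopsis and Table 1 as the incidence of adverse events from first dose through the EoS (Week 21) visit, comprising TEAEs and post-treatment events.
3. Add treatment-period, follow-up and total columns to the adverse event overview and SOC/PT tables, and preferably to the AESI table. Count each participant once in the total.
4. State that events first reported at the Week 29 call with onset after EoS are listed outside this total, consistent with follow-up ending at Week 21.

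The cost is small wording edits and a few table columns. Compared with the TEAE figure alone, the reported incidence can only stay the same or rise. A footnote should say that the total window (140 days as scheduled) is longer than the counted exposure (112 days). Because the TEAE period does not move, the vital-sign window and the missing-date rule are unaffected.
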